**Primary analysis for Trial II.** The primary outcome for Trial II is the proportion of participants experiencing CMV recurrence over 12 months. We acknowledge that hypothesizing fewer recurrences in the placebo group compared to the oral antiviral group is contradictory to what one might think would typically occur with exposure to antivirals. However, data from a previous observational study showed a one-year recurrence risk of 25.0% (3/12) among participants who did not receive antiviral treatment and 75.0% (9/12) in participants receiving systemic antiviral treatment (oral ganciclovir or valganciclovir), which is similar to the experience of other research. Additionally, it is well documented that long-term suppressive-level dosing of antiviral in an immunodeficient host or in an immunologically privileged organ (such as the eye) can create an environment permissive to the development of antiviral resistance. Given 28 participants per arm (105 total from Trial I with 20% loss to follow-up) and a recurrence risk of 25% in the placebo group, we can detect a difference of 40 percentage points between the oral valganciclovir and the placebo groups (from 25% to 65%), using a two-sample z-test for proportions with 80% power and a two-sided alpha of 0.05/2.

**For Specific Aim 3,** we estimated the minimum detectable effect for the difference in prevalence of infections that have antiviral resistance mutations among recurrent infections in Trial II among patients who receive long-term antiviral prophylaxis compared with their infections at baseline. Aim 3 will focus on patients in the two active treatment arms in Trial II, because we would expect long-term use of topical and oral antivirals to lead to similar selection for antiviral resistance. From 117 patients enrolled, we conservatively assumed that 72% of patients would complete both Trial I and Trial II (n=84). We further assumed that 60% of patients will develop a recurrent infection over the monitoring period during the trials (Table 1). Participants who receive active treatment in Trial II (treatment regimens C+D) will contribute to the Aim 3 analysis (n=34). The analysis will be a paired analysis, comparing the proportion of recurrent infections with antiviral resistance mutations with that same proportion at baseline.

Table 1. Anticipated participant enrollment, and follow-up by treatment patterns

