Treatment Pattern, Trial I → Trial II	Number enrolled	Number completing Trial I (assumed 90%)	Number completing Trial I and Trial II (assumed 80% from Trial I)	Number with Recurrent Infections in Trial II, included in Aim 3 (assumed 60%)
A. Placebo → Placebo	13	12	10	
B. Treatment → Placebo Topical g. → Placebo Oral v. → Placebo	26	23	18	
C. Placebo → Treatment Placebo → Topical g. Placebo → Oral v.	26	23	18	11
D. Treatment → Treatment Topical g. → Topical g. Topical g. → Oral v. Oral v. → Topical g. Oral v. → Oral v.	52	47	38	23
Total	117	105	84	34

In the absence of longer-term antiviral therapy, we anticipate 5% of patients would experience recurrent infections with antiviral resistance mutations. A recent analysis of 2750 transplant recipients identified 30.4% patient samples had resistance to anti-CMV drugs. We assumed 80% power and a two-sided alpha of 0.05. Under these assumptions, we estimate that we will be able to detect a 25% increase in the percentage of infections with antiviral resistance genes (from 5% to 30%), using a two-sample z-test for proportions with equal sample sizes. We note this detectable effect is conservative because it ignores possible correlation within-individuals in the paired outcomes, which would increase our power.

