**Aim 3. Prevalence of mutations conferring antiviral resistance:** The analysis population will include individuals enrolled in both Trials I and II who are randomized to receive oral or topical antivirals in Trial II and experience a recurrent infection. Among patients that experience a recurrent infection (anticipated n=34, see Sample Size section 3.3), we will compare the proportion of infections with antiviral mutations upon recurrence with the proportion with antiviral mutations at baseline. The analysis will thus be a pair-matched analysis (within-patient). We will use a linear binomial model to estimate the difference in prevalence of resistant infections, including fixed effects for each participant that will control for all between-participant characteristics in this observational analysis. Additional covariates in the model will include treatment arm and site. This pair-matched analysis is similar to McNemar's test, but allows us to control for type of retroviral and enrollment site using regression.

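### SAP 6.2 Aim 3: the arm and site terms cannot be estimated beside participant fixed effects, and the unnamed estimator matters, because a binomial-likelihood fit is pulled to zero at the design effect

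*SAP*

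**What the plan says.** SAP 6.2, Aim 3, compares resistance mutations at recurrence in Trial II with those at Trial I baseline, within participant, in those on active Trial II treatment who recur. The model reads: "We will use a linear binomial model to estimate the difference in prevalence of resistant infections, including fixed effects for each participant". It continues: "Additional covariates in the model will include treatment arm and site". The section likens this to McNemar's test and gives control for drug type and site as its advantage. It names no estimation method and no interaction of arm or site with sampling time.

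SAP 3.3 expects 34 such participants. On the base rate it says "we anticipate 5% of patients would experience recurrent infections with antiviral resistance mutations", in the absence of longer-term therapy. On the target it says "we estimate that we will be able to detect a 25% increase in the percentage of infections with antiviral resistance genes", from 5% to 30%, by an unpaired two-sample z-test. On error rates: "We assumed 80% power and a two-sided alpha of 0.05". SAP 4.1 lists resistance mutations as a key secondary endpoint, tested only after the primary endpoints succeed. The Sensitivity Analyses paragraph of SAP 6.2 provides for unspecified alternative models if fit is inadequate.

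**The concern.** There are two separate problems.

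First, a participant indicator already absorbs everything that does not change between that participant's two samples. Trial II arm and enrolment site do not change, so adding them as main effects adds nothing.

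Second, one free intercept per participant with only two binary results each is a setting where maximum likelihood need not converge to the truth. On the identity scale, pairs that do not change are best fitted by a change of zero. They should carry no information on direction, yet they pull the common difference towards zero.

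At stake is whether the pre-specified analysis can show the rise in resistance that Aim 3 is sized to find. Resistance under long-term antivirals is also part of the SAP's argument for its Trial II hypothesis.

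**Working it through.** **Inputs.** From SAP 3.3: 34 pairs, 5% and 30%, two-sided alpha 0.05, 80% power. From the Protocol synopsis: 6 sites. The within-pair correlation is not given, so I took the feasible range, writing p01 for the probability of becoming resistant and p10 for reverting:
- nested: p01 = 0.25, p10 = 0
- independent: p01 = 0.95 × 0.30 = 0.285, p10 = 0.05 × 0.70 = 0.035
- least overlap: p01 = 0.30, p10 = 0.05

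**The plan's own figure.** The pooled two-sample z-test of 5% against 30% needs 36 per group. With 34 its power is 0.787 (0.819 unpooled). The 25-point figure reproduces.

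**Rank.** 34 participant columns + 1 sampling-time column + 1 arm column + 5 site columns = 41 columns; the rank is 35. The 41 − 35 = 6 missing dimensions are the arm and site coefficients. The sampling-time contrast is estimable. Coding arm as none at baseline and oral or topical at recurrence, beside a time term, is still deficient (37 columns, rank 36).

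**Binomial likelihood.** Let a participant's probability be a at baseline and a + d at recurrence, with d ≥ 0. Maximising over a gives each pair's contribution:
- unchanged (00 or 11): 1 − d
- newly resistant (01): ((1 + d)/2)²
- reverted (10): ((1 − d)/2)²

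With nc concordant pairs, the profile log-likelihood is, up to a constant, (nc + 2·n10)·log(1 − d) + 2·n01·log(1 + d). Its slope at d = 0 is 2·n01 − nc − 2·n10. So the estimate is positive only if 2(n01 − n10) > nc, and then equals (2·n01 − nc − 2·n10)/(2·n01 + nc + 2·n10). A grid search on the likelihood agrees.

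| New / reverted, of 34 | Paired difference (n01 − n10)/34 | Likelihood estimate |
|---|---|---|
| 9 / 0 | 0.265 | 0 (2×9 = 18 < 25) |
| 10 / 1 | 0.265 | 0 (2×9 = 18 < 23) |
| 12 / 0 | 0.353 | (24 − 22)/(24 + 22) = 0.043 |
| 17 / 0 | 0.500 | (34 − 17)/(34 + 17) = 0.333 |

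**At the design effect (5% to 30%).** Twice the expected net switches is 2 × 34 × 0.25 = 17 in all three cases, always below the concordant count.

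| | Nested | Independent | Least overlap |
|---|---|---|---|
| Expected new / reverted | 8.5 / 0 | 9.7 / 1.2 | 10.2 / 1.7 |
| Expected concordant pairs | 25.5 | 23.1 | 22.1 |
| Estimate at expected counts | 0 | 0 | 0 |
| Trials with estimate exactly 0 | 88% | 79% | 75% |
| Mean likelihood estimate | 0.012 | 0.022 | 0.028 |
| Mean paired difference | 0.25 | 0.25 | 0.25 |

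For a net 25 points to give a positive estimate, concordant pairs would have to fall below 17, which needs more than (17 − 8.5)/2 = 4.25 reversals. A 5% base rate allows at most 0.05 × 34 = 1.7 on average. The likelihood-ratio test has power of 0.4% to 1.5%.

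**In R, the SAP's software.** With new/reverted counts of 8/0, 10/1 and 9/0, the identity-link binomial fit as specified stopped for want of valid starting values. With starting values supplied and arm and site removed, it converged to 0.001 to 0.004. Least squares gave 0.235 to 0.265 and returned no value for any of the six arm and site coefficients.

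**Power of paired tests, n = 34, two-sided alpha 0.05.**

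| | Nested | Independent | Least overlap |
|---|---|---|---|
| Asymptotic McNemar | 0.98 | 0.79 | 0.74 |
| Mid-p McNemar | 0.95 | 0.79 | 0.735 |
| Exact McNemar | 0.89 | 0.70 | 0.65 |

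**The case against.** A reader might infer that the whole Aim 3 model is unidentified. The documents do not support that. Only the arm and site coefficients are lost; the contrast of interest is estimable, and the participant effects already absorb arm and site. The terms are redundant, and the error is the claim that they add control.

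A reader might also infer that the plan as written will report no change when resistance rises to 30%. That goes too far for three reasons:
- The SAP does not say that the model is fitted by binomial likelihood. The likeness to McNemar's test, and the choice of linear or log-binomial regression for Aim 1b, are compatible with least squares, which gives the right answer.
- Even under likelihood the zero is not certain in a given trial; it occurs in 75% to 88%.
- The fit as specified may stop with an error instead of quietly returning zero, and the SAP allows alternative models.

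These points limit the claim but do not remove it. The word binomial points to the likelihood reading, and the two readings give about 25 points or about 0 from the same data. The clause on alternative models names nothing for Aim 3, so the estimator would be chosen after the data are seen.

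**Conclusion.** The point holds in two parts. Under any fitting method, the stated control for drug type and site cannot come from main effects beside participant fixed effects. Under identity-link binomial maximum likelihood, the natural but not the only reading, the estimate at the design effect is 0 at the expected counts and averages 0.012 to 0.028 against a true 0.25. Under least squares the estimate is correct.

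The sizes rest on 34 complete pairs, the SAP's 5% and 30%, and the assumed range of within-pair correlation. Severity is should-fix: this is a gated key secondary, and both primary analyses are untouched.

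**What to change.** In SAP 6.2, Aim 3, name the estimator as the paired difference in proportions, (n01 − n10)/n, with a paired score 95% interval and a mid-p (or asymptotic) McNemar test. Least squares with participant effects and robust standard errors gives the same estimate and is an acceptable alternative if named as such. Delete the arm and site main effects and the sentence that claims control for them. If arm matters, use a visit-by-arm interaction or report the paired difference by arm.

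The cost is SAP wording only; no data or visits change. The downside to state is that power depends on the unknown within-pair correlation and can fall below 80%. An exact test would be the costlier choice (0.65 to 0.89, against about 0.74 to 0.95 for mid-p).

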### Sensitivity Analyses

In all analyses, model adequacy will be checked by examination of residuals or other goodness of fit tests as needed. Inadequate model fit will prompt us to report alternative models. If there are chance imbalances in prognostic baseline patient characteristics, including age, sex, and prednisolone use prior to enrollment, a secondary analysis will include them as covariates in the regression model.

## 6.3. Missing data handling

In Trial I and Trial II, we will report the fraction missing or lost to follow-up by study arm. If  $\leq 10\%$  of enrolled participants are missing outcome data, complete case analyses will be conducted. If  $> 10\%$  of enrolled participants are missing outcome data, inverse probability weighting will be used to weight complete cases by the inverse of an estimate of the probability of an outcome being observed as a sensitivity analysis. Weights will be constructed with baseline characteristics likely to predict missingness that are also associated with the outcome, including primary variables (viral load measurements, time to recurrence, treatment assignment, site) and auxiliary variables (baseline characteristics, partial outcome data, adherence measures, prior treatment history).

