#### 3.3. Sample size

**Primary analysis for Trial I.** The power calculation was based on the primary outcome, base-10 logarithm-transformed CMV viral load. We informed the calculation with viral loads from our recently completed RCT, in which we measured viral load at baseline and 7 days post-treatment. The standard deviation (SD) of log-transformed viral load 7 days post-treatment in this RCT was 0.98. Since the primary analysis will adjust for baseline viral load, we used an estimate of the residual standard deviation, which is  $SD_r = SD\sqrt{1 - r^2}$ , where  $r$  is the correlation between the baseline measure and primary endpoint. In our recently completed RCT, the correlation between baseline and post-treatment viral load was 0.74. Assuming a significance level of 0.05/2=0.025 to account for multiple comparisons and an  $SD_r$  of 0.66 in  $\log_{10}$  viral load, we estimate that we will have 80% power to detect a difference of 0.50 in  $\log_{10}$  viral load (from

3.11 to 2.61) between arms with 35 study participants per arm (117 total allowing for approximately 10% loss to follow up). A reduction of 0.50 in  $\log_{10}$  viral load is equivalent to a  $10^{0.50} = 3.2$ -fold decrease in CMV viral load, which is small but clinically meaningful in the context of CMV antivirals that typically consider 10-fold reductions. This calculation is based on the standard power formula for the T-test using an estimated residual standard deviation.

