### Primary Analysis Trial I

*Aim 1a.* The primary analysis will compare **viral load at 7 days** between each study arm. The Aim 1 treatment effect will be reported as a difference in log IU/mL between the two arms.

We will model mean log viral load using linear regression that includes indicators for treatment arm, indicators for each site used to stratify the randomization, and baseline viral load. We will additionally estimate max-T simultaneous confidence intervals and p-values adjusted for the two

pair-wise comparisons (*oral valganciclovir* vs. *topical ganciclovir 2%*, *oral valganciclovir* vs. *placebo*).

We will examine residuals for approximate normality and to check for outliers and will report the variance within each arm.

Primary analyses will be repeated using multiple imputed datasets as described in Section 6.3 when missing data thresholds are met.

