### Secondary Analyses Trial II

**Aim 2b. Prevalence of detectable CMV with recurrence.** The proposed outcome for Aim 2b is prevalence of detectable CMV (CMV positive) based on nucleic acid amplification testing obtained from anterior chamber fluid (aqueous humor) obtained at recurrence during Trial II. Thus, this sub-aim is a microbiologic outcome. We will calculate the proportion of recurrence episodes with detectable CMV viral load by using log-binomial regression with treatment arm indicators and site stratification. We will report adjusted confidence intervals and p-values for treatment arm comparisons. For correlation between viral load and inflammation, we will assess the relationship between log-transformed viral load and anterior chamber cell grade at recurrence of inflammation using a log-binomial regression model adjusting for treatment arm and site. Pre-specified subgroup analyses by sex will be performed for both components. We will handle missing data through sensitivity analyses using multiple imputation.

**Aim 2c. Time to first CMV anterior uveitis recurrence within 12 months.** An exploratory outcome of Trial II will be the time to first CMV anterior uveitis recurrence within 12 months. We will use a Cox proportional hazards model to compare the time to recurrence by the arm within the 12 months of long-term suppressive therapy, including an indicator for each treatment arm and an indicator for site. We will assess the proportional hazards assumption by examining Kaplan-Meier curves by treatment group on the original and log-log scales and will examine Schoenfeld residuals to assess model fit. We will estimate the hazard ratio from the model for the two primary comparisons, *oral valganciclovir* vs. *topical ganciclovir 2%*, *oral valganciclovir* vs. *placebo*. Both comparisons will use max-T adjusted p-values and simultaneous 95% confidence intervals. Sensitivity analyses will examine 1) alternative censoring assumptions and 2) time-varying hazards if proportional hazards assumption is violated.

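### SAP Section 6.2 relies on a multiple imputation that Section 6.3 does not contain, and the weighting that Section 6.3 does describe cannot be run as written in Trial II

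*SAP*

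**What the plan says.** The documents give three accounts of what happens when outcomes are missing.

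- **SAP Section 6.2, Primary Analysis Trial I:** "Primary analyses will be repeated using multiple imputed datasets as described in Section 6.3 when missing data thresholds are met".
- **SAP Section 6.3:** complete-case analysis if no more than 10% of enrolled participants lack outcome data. Above 10%, "inverse probability weighting will be used to weight complete cases by the inverse of an estimate of the probability" of being observed, labelled a sensitivity analysis. The weights are introduced as built from baseline characteristics, "including primary variables (viral load measurements, time to recurrence, treatment assignment, site"), followed by auxiliary variables that include partial outcome data and adherence measures.
- **Protocol Section 8.3, Population for Analyses:** a complete-case analysis, a sensitivity analysis that fills in outcomes for those missing, and analyses adjusted for baseline predictors of missingness. It refers to the SAP for details.

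For Aim 2b, a secondary analysis, SAP Section 6.2 again names imputation: "We will handle missing data through sensitivity analyses using multiple imputation". Aim 2c in the same section makes time to first recurrence an exploratory outcome of Trial II.

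**The concern.** There are two faults.

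First, the cross-reference from 6.2 to 6.3 leads to a different method. Section 6.3 has no imputation model, number of imputations or pooling rule. The SAP reference list includes a paper on chained-equations imputation that no section cites in the text available, which suggests a description that is no longer there. An analyst would have to choose between methods, possibly after seeing the data.

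Second, a model for the probability that an outcome is observed needs covariates known both for people with the outcome and for people without it. Time to recurrence fails this in Trial II. The listed variables would suit an imputation model better than a weight model.

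At stake is the check on attrition in Trial II, whose plan expects one participant in five to be lost. As written, that check would either fail to fit or repeat the complete-case estimate, and the agreement would look reassuring without meaning anything.

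**Working it through.** **1. The plan's own sizes (SAP Section 3.3).**

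Trial I inputs: "The standard deviation (SD) of log-transformed viral load 7 days post-treatment in this RCT was 0.98"; "the correlation between baseline and post-treatment viral load was 0.74"; "Assuming a significance level of 0.05/2=0.025 to account for multiple comparisons"; "80% power to detect a difference of 0.50 in" log10 viral load.

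- Residual SD = 0.98 × √(1 − 0.74²) = 0.659, stated as 0.66.
- Two-sample t-test at two-sided alpha 0.025: 34 per arm gives 79.5% power and 35 gives 80.8%. The stated 35 is reproduced.
- Loss of 10%: 35 / 0.90 = 38.9, rounded up to 39; 39 × 3 = 117. Reproduced.

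Trial II: 105 × 0.80 = 84, or 28 per arm. Reproduced.

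**2. Does the planned loss pass the trigger (strictly more than 10%)?**

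| | Enrolled | Completing | Planned missing | Smallest count over 10% |
|---|---|---|---|---|
| Trial I | 117 | 105 | 12/117 = 10.26% | 12 (10% of 117 = 11.7) |
| Trial II | 105 | 84 | 21/105 = 20.0% | 11 (10% of 105 = 10.5) |

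Trial I passes 10% only through rounding to whole patients (105 / 0.90 = 116.7, taken as 117). At the stated rate of 10% it does not.

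Treating losses as independent, the binomial chance that the rule fires is:

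- Trial I, 12 or more of 117 missing: 23% if the true loss is 8%, 51% if 10%, 76% if 12%.
- Trial II, 11 or more of 105 missing: 99.7% if the true loss is 20%.

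**3. Can the weights be estimated in Trial II?**

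Let R = 1 if the 12-month recurrence outcome is observed. The weight is 1 / P(R = 1 | covariates). For someone lost before recurring, R = 0 and time to recurrence is unknown. A regression that includes it therefore drops every row with R = 0.

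An illustrative simulated Trial II set (105 entered, 21 lost) shows the result. With baseline viral load and time to recurrence as covariates, 84 rows are usable and all have R = 1. The logistic fit does not converge, its parameters are not identified, and the fitted probabilities are about 1. Every weight is then about 1, and the weighted estimate equals the complete-case estimate. With baseline viral load alone, supposed known for everyone in the simulation, the model fits on all 105, with fitted probabilities from 0.772 to 0.823.

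Replacing time to recurrence by last follow-up time plus a recurrence indicator does not help. The outcome is observed exactly when a recurrence is seen or 12 months are completed, so those two variables together predict R perfectly.

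**4. Is viral load known for everyone in Trial II?**

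No. The protocol's Schedule of Activities has no paracentesis at Trial II Exam 1, and Section 7.1.2 takes Trial II fluid only at recurrence. Protocol Section 4.1 also lets inactive patients enter Trial II directly, and they have no Trial I sample.

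**The case against.** Several stronger readings are tempting, and the documents do not support them.

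- **That both trials' planned losses trigger the rule.** The stated Trial I assumptions are approximately 10% loss and 90% completion, and the trigger is strictly more than 10%. Trial I is about as likely as not to fire; only Trial II is clear.
- **That the weights use the missing outcome in both trials.** Section 6.3 speaks of baseline characteristics. Fluid for quantitative PCR is kept from Exam 0, and the Trial I primary model already adjusts for baseline viral load. If viral load measurements means the baseline value, the Trial I weighting can be run, since time to recurrence has no meaning there. Against this reading, the list names baseline characteristics again as a separate auxiliary item, so the wording remains unclear.
- **That the primary analysis is undermined, or that no other attrition check exists.** Weighting is labelled a sensitivity analysis. A complete-case analysis can still be run, and the protocol plans two further checks.
- **That imputation and weighting cannot coexist.** They can, as two sensitivity analyses. Naming imputation for Aim 2b does not by itself contradict weighting for a primary outcome.

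All four limits stand. None of them supplies the imputation method that Section 6.2 refers to, or makes time to recurrence known for participants lost before recurring.

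**Conclusion.** The point holds as a fault in the SAP's missing-data sensitivity analysis. The reference from 6.2 to 6.3 is broken, the protocol adds a third approach that the SAP does not take up, and the weight model mixes outcome and post-baseline variables into a list described as baseline.

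The failure is firm for Trial II. If time to recurrence is entered as listed, the weights cannot be estimated or are constant, and the planned 20% loss means the rule would almost certainly be invoked (99.7% if the true loss is 20% and losses are independent). For Trial I the rule sits on its threshold (51% at a true loss of 10%), and its weighting is usable if the viral load in the list is the baseline value.

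The stated sample sizes reproduce and are not affected. This should be corrected before unmasking, but it does not threaten the main complete-case results.

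**What to change.** Make SAP Section 6.2, SAP Section 6.3 and the protocol's Population for Analyses text agree on the missing-data sensitivity analysis. Two routes are open.

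1. **Imputation.** Describe multiple imputation in 6.3, using the listed primary and auxiliary variables. Give the model, the number of imputations and the pooling rule. State the missing-at-random assumption, and say how the binary Trial II outcome is derived consistently from time to recurrence, since one determines the other.
2. **Weighting.** Keep inverse probability weighting, and limit the weight model to variables known for every participant randomised in that trial: arm, site, age, sex and prior treatment history, plus baseline viral load in Trial I only. Remove time to recurrence, the outcome viral load and the other post-baseline items. A Trial I viral load should enter the Trial II model only if the SAP says how direct entrants, who have none, are handled.

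If both methods are kept, describe each in 6.3 and say which outcome each serves. Say also how the protocol's filled-in-outcome analysis fits alongside them.

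The cost is SAP and protocol wording only, with no change to sample size, visits or data collection.
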